## Version Tracking

Version	Date	Authors	Comments
0.0.1	03 Nov 2014	MH, DW, NG, EMac	Draft reviewed by WG at November 12 planning meeting
0.0.2	17 Dec 2014	JHF	Incorporated WG comments and added more detail to sections on study procedures and data forms in preparation for GN Investigator review
0.1.0	18 Dec 2014	NG, JHF	Minor revisions. This version will be sent to GN investigators for initial review.
0.1.1	10 Jan 2015	JHF in response to PI/SFI review	
 
▪ Made revisions to improve clarity and fix grammar/spelling as suggested by reviewers.
 
▪ Incorporated comments from [name], [name], [name], [name], [name], [name] that need to be discussed further.
 
▪ Updated Sample Size section to consistently note a 20% reduction instead of 25%.
 
▪ Added secondary outcomes from the survey responses.
 
▪ Added comments and information from the survey responses for discussion/consideration by WG.
 

0.2.0	19 Jan 2015	JHF and MH	
 
▪ Finalized revisions from all reviewers. This version was circulated to GN Investigators in advance of the Jan SC meeting.
 

0.2.1	29 Jan 2015	JHF and MH	
 
▪ Revisions based on investigator feedback at SC Meeting
 

0.2.2	06 Feb 2015	JHF	
 
▪ Further revisions based on investigator and WG feedback
 

0.2.3	12 Feb 2015	JHF/RTI	
 
▪ Revisions based on internal review at RTI
 

0.3	16 Feb 2015	Aspirin WG	
 
▪ Updates to language re: pill packaging, anemia monitoring, sample size. Appendix 2 and 3 added.
 

0.3.1	19 Feb 2015	NICHD	
 
▪ Suggestions from [name] and [name]
 

0.3.2	20 Feb 2015	NICHD, MH, RD, RTI	
 
▪ Revisions based on group review
 

0.3.3	24 Feb		
 
▪ Updated based on group review
 

0.3.4	26 Feb	NICHD, MH, BM, JH	
 
▪ Updates following protocol review
 

0.3.5	05 Mar 2015	MKT, DW, JHF	
 
▪ Updates to Section 2.3 (study flow chart), Section 2.4.3.1 (Assigning EDD), Section 2.11 (Risk/benefit), Section 3. (Secondary analysis, DSMB/DMC description), Section 4 (form description).
 

0.4.0	09 March 2015	SG, MKT, JHF	
 
▪ Revised sample consent, updated secondary outcome to include perinatal mortality.
 

1.0	10 March 2015	WG	
 
▪ Final revisions to fix consistency issues. This is the version circulated to sites for IRB/EC submission.
 

1.1	21 March 2015	JHF	
 
▪ Removed “perinatal mortality and morbidity” from the Section 1.1 (Primary Hypothesis or Problem).
 
▪ This version was sent to the sites to replace version 1.0 for IRB submission.
 

1.2	05 Dec 2016	NG	
 
▪ Included ClinicalTrials.gov number, added protocol number, made hypertension exclusion explicit with definition, updated site information and fixed minor typographical errors.
 

1.3	21 Feb 2019	NG	
 
▪ Replaced ‘heart rate greater than 110 bpm’ with ‘presence of a heartbeat’ in Section 2.2.1 Inclusion Criteria.
 
▪ Added ‘(hypertensive disorders of pregnancy)’ to Preeclampsia and eclampsia in Section 2.6 Secondary Outcomes for clarification.
 
▪ Included ‘Preterm, preeclampsia’ in Section 2.7 Other outcome of interest – Maternal outcomes.
 

## ACRONYMS

---

ACOG	American Congress of Obstetricians and Gynecologists
APS	Antiphospholipid syndrome
ASA	Acetylsalicylic acid
BP	Blood pressure
CLASP	Collaborative Low-dose Aspirin Study in Pregnancy
COX	Cyclo-oxygenase
CRL	Crown rump length
DCC	Data Coordinating Center
DMC	Data monitoring committee
DMS	Data Management System
DRC	Democratic Republic of Congo
EAGER	Effects of Aspirin in Gestation and Reproduction Study
EDD	Estimated due date (or estimated date of delivery)
ERC	Ethical review Committee
GA	Gestational age
GN	Global Network for Women's and Children's Health Research
Hb	Hemoglobin
JNMC	Jawaharlal Nehru Medical College
IRB	Institutional Review Board
IUGR	Intrauterine growth restriction
LBW	Low birth weight
LDA	Low dose aspirin
LMP	Last menstrual period
MNH	Maternal and Newborn Health
NICHD	Eunice Kennedy Shriver National Institute of Child Health and Human Development
NIH	National Institutes of Health
NSAID	Non-steroidal anti-inflammatory drug
PIH	Pregnancy induced hypertension
PMNCH	The Partnership for Maternal, Newborn, & Child Health
PROM	Premature rupture of membranes
PTB	Preterm birth
RCT	Randomized controlled trial
RTI	Research Triangle Institute International
SAE	Serious adverse event
SFI	Senior Foreign Investigator
SGA	Small for gestational age
SPTB	Spontaneous preterm birth
VLBW	Very low birth weight
WHO	World Health Organization

## ABSTRACT

---

**Background:** Preterm birth (PTB) remains the leading cause of neonatal mortality and long term disability throughout the world. Though complex in its origins, a growing body of evidence suggests that first trimester administration of low dose aspirin (LDA) holds promise to reduce the rate of PTB substantially.

**Hypothesis:** First trimester administration of aspirin will reduce the risk of preterm birth.

**Study Design Type:** Prospective randomized, placebo-controlled, double-blinded multicenter clinical trial. Trial will be individually randomized with one-to-one ratio (intervention/control)

**Population:** Nulliparous women between the ages of 18 and 40, with a singleton pregnancy between 6 0/7 weeks and 13 6/7 weeks gestational age (GA) confirmed by ultrasound prior to enrollment, no more than two previous first trimester pregnancy losses, and no contraindications to aspirin. Minors who are  $\geq$  14 years of age may be enrolled if permitted by the country's ethical guidelines.

**Intervention:** Daily administration of low dose (81 mg) aspirin [also known as acetylsalicylic acid (ASA)], initiated between 6 0/7 weeks and 13 6/7 weeks GA and continued to 36 0/7 weeks GA, compared to an identical appearing placebo. Compliance and outcomes will be assessed biweekly.

**Outcomes:**

**Primary outcome:** To determine whether daily LDA initiated between 6 0/7 -13 6/7 weeks GA and continued to 36 0/7 weeks GA reduces the risk of PTB (birth prior to 37 0/7 weeks GA).

**Secondary outcomes** of interest are the rate of preeclampsia/eclampsia, small for gestational age (SGA), and perinatal mortality.

# 1 STATEMENT OF PROBLEM

---

## 1.1 PRIMARY HYPOTHESIS OR QUESTION

Our primary hypothesis is that nulliparous women with no more than two previous first trimester pregnancy losses who are treated with LDA daily beginning between 6 0/7 weeks and 13 6/7 weeks GA through 36 0/7 weeks GA will reduce the rate of preterm birth from all causes.

## 1.2 SECONDARY HYPOTHESIS

Women who take antenatal daily LDA initiated at 6 0/7 to 13 6/7 weeks GA will have lower rates of:

- Small for gestational age (SGA)
- Eclampsia and preeclampsia
- Perinatal Mortality

## 1.3 BACKGROUND AND RATIONALE

Preterm delivery, defined as delivery prior to 37 weeks 0/7 days gestation, remains the dominant cause of neonatal morbidity and mortality throughout the world and directly leads to 28% of neonatal deaths within the first seven days of life. Moreover it is responsible of up to 50% of pediatric neurodevelopmental disorders. Infants born prematurely are likewise at increased risk for a variety of long term medical complications such as respiratory, gastrointestinal, cardiovascular, and metabolic disorders.

Compounding the issue, the risk of preterm birth is highest in developing countries where an estimated 12% of births are preterm compared to 5-7% in developed countries. Of the near 13 million preterm births worldwide in 2005, 11 million were in Africa and Asia. Given the tremendous medical, financial and emotional burden of preterm birth in the developing world and the limited resources to provide postnatal care, any interventions with the potential to reduce the rate of preterm birth deserve consideration. If one were to choose an intervention, it would be one that is widely available, inexpensive, and safe for the mother and fetus. Low dose aspirin may be just such an intervention.

### 1.3.1 Biology of Aspirin in Pregnancy

Aspirin is best known for its analgesic properties; however, it is well documented that aspirin is an anti-inflammatory and potent inhibitor of platelet aggregation, contributing to its anti-thrombotic effects. Both inflammation and thrombosis have been demonstrated to be the pathways responsible for the majority of preterm birth, preeclampsia and fetal growth restriction. The primary biologic effects of aspirin are mediated by inhibition of the enzyme cyclooxygenase (Cox), which produces substances known to be involved in the defined pathways of preterm birth and placental dysfunction (Preeclampsia/growth restriction/stillbirth). By decreasing these mediators and in turn decreasing inflammation and placental dysfunction due to thrombosis, aspirin may reduce the rates of the major obstetrical complications of preterm birth, preeclampsia and growth restriction.

Equally important to the mechanisms by which Aspirin works, may be the time frame in which it is initiated. Biologically it has been demonstrated that the process of preterm birth generally begins prior to 16 weeks . Likewise placental invasion of the maternal decidua is noted to occur in the first trimester and underlies the pathologic processes of preeclampsia and pathologic growth restriction. Thus aspirin may be maximally effective if initiated in the first trimester as proposed in this study.

### **1.3.2 Aspirin & Preterm Birth**

Though the available evidence is promising, data regarding the early use of aspirin in pregnancy to prevent preterm birth are limited to two main sources: (1) Meta-analyses of prior trials and (2) a single trial of preconception aspirin (Effects of Aspirin in Gestation and Reproduction (EAGeR) Study). Multiple meta-analyses have been performed showing a limited impact on preterm birth. For example Roberge, in a meta-analysis of LDA included 22 trials that included 11,302 women, found a 19% reduction in the overall rate of preterm birth (RR 0.81, 95% CI 0.71 to 0.92) . When this meta-analysis was restricted to women who initiated aspirin prior to 16 0/7 weeks a 65% reduction was observed (6 trials including 904 women, RR 0.35, 95% CI to 0.22 to 0.57).

The EAGER trial shows similar trend towards risk reduction in a cohort of 1,078 women who were randomized to LDA prior to conception. If only the original cohort (women with just one prior loss or less) is examined, there is a 55% reduction in preterm birth (RR 0.45; p-value of 0.087). When expanded to include the entire cohort (includes women with more than one fetal loss), there is a 28% risk reduction (RR of 0.72; p value 0.260). The lack of significant difference in this trial is not surprising as the primary outcome was not preterm delivery and the low risk nature of the enrolled women . Nonetheless, the point estimates of the sole prospective pre conception LDA trial (EAGeR) and the multiple meta-analysis of women who initiated LDA early, suggest that LDA is associated with a decrease in the rate of PTB between 28% and 65%.

### **1.3.3 Aspirin & Preeclampsia**

Many large randomized controlled clinical trials have been conducted in both high and low risk populations (with regard to the development of preeclampsia). Duley and colleagues performed a systematic review that included 51 trials involving 36,500 women treated with antiplatelet agents for the prevention of preeclampsia . Forty-four of these trials involved the use of aspirin alone (compared with placebo or no treatment) while the remainder included other treatments, often in conjunction with aspirin. Overall, the use of antiplatelet agents conferred a 19% reduction in the risk of preeclampsia (RR 0.81; 95% CI, 0.74-0.96). There was a greater risk reduction in women treated with doses greater than 75 mg/day (RR 0.49, 95% CI 0.38-0.65) compared to lower doses (RR 0.86, 95% CI 0.79-0.93). Others reviews emphasize the increased benefit from LDA in women with historical risk factors (high risk for preeclampsia) and suggest that focusing on at risk groups would decrease the number of women it is necessary to treat to prevent a single case of preeclampsia . Like prematurity, one sees a difference in effect size based on the time of initiation. Roberge in a meta-analysis of 33 trials found a risk reduction of 0.62 (0.49 to 0.78); however, when this was restricted to women who began therapy <16 weeks the effect size was much greater (RR 0.47 (0.36 to 0.62). Of course, the “risk: benefit” ratio also is influenced by risk, which appears to be quite low for LDA. Thus, treatment of low risk women may yet prove to be justified.

### **1.3.4 Aspirin & Growth Restriction (Small for Gestational Age)**

Low dose aspirin (LDA) also may reduce the risk of other adverse perinatal outcomes such as small for gestational age (SGA) fetus and late fetal death. In 32 trials of 24,310 women, antiplatelet therapy conferred an 8% reduction in SGA (RR 0.92, 95% CI 0.85-1.00) in women treated with the intent to prevent preeclampsia . A small trial showed no benefit from LDA in women treated after the diagnosis of SGA fetus . LDA also has not been effective when started after the diagnosis of preeclampsia . Once again early initiation may be the key to success. Roberge in a like meta-analysis found a modest impact of LDA on growth restriction (RR 0.86, 95%CI 0.75-99); however when only women who initiated therapy at or before 16 weeks were examined the effect size was markedly more pronounced (0.46, 95%CI 0.33-0.66).

The review by Duley and colleagues noted a 16% reduction in combined fetal, neonatal, and infant mortality in women taking antiplatelet therapy (RR 0.84, 95% CI 0.74-0.96). Perinatal death and SGA fetuses were not primary end points of these trials and results should be interpreted with caution.

### **1.3.5 Aspirin safety**

Low dose aspirin is interesting as a potential therapy for reproductive disorders because it has a demonstrated track record of both fetal and maternal safety. Randomized controlled trials (RCTs) in thousands of women showed no increase in adverse fetal sequelae in doses < 150 mg per day . In a meta-analyses of 22 studies, aspirin was not associated with an overall increase in the risk of congenital malformations . The same meta-analysis reported an increase in the risk of gastroschisis (OR 2.37; 95% CI, 1.44 – 3.88) in infants exposed to high-dose aspirin (325 mg per day) in the first trimester . This is biologically plausible since this malformation may be caused by vascular disruption of mesenteric vessels . Results were not confirmed in a recent population based case-control study  and the association between aspirin use and gastroschisis remains uncertain. Indeed, aspirin is often used empirically to treat infertility, recurrent miscarriage and Antiphospholipid syndrome (APS). Studies regarding safety are difficult to compare due to different doses, duration, and timing of aspirin use (with regard to pregnancy). Nonetheless, the majority of data indicates minimal fetal risk from *in utero* LDA exposure. In fact, a recent study noted that LDA was actually associated with a reduction in neurobehavioral difficulties in very preterm infants .

### **1.3.6 Summary**

We intend to study the effects of LDA in nulliparous women for several reasons. First, although it would be of interest to study the effect of LDA in women at high risk for preterm birth (e.g. prior preterm birth), such women may undergo interventions intended to decrease their risk of preterm birth. Thus, a study in patients with prior preterm birth would have numerous potential confounders. Conversely, multiparous women with prior term births would be at very low risk for preterm birth and also be a suboptimal population to study. Nulliparous women appear to be an ideal population since they will not undergo special interventions in an attempt to avoid preterm birth. Also, it appears that the risk of preterm birth in nulliparous women is higher than for the general obstetric population. In summary, available data suggest that LDA may be a safe, widely available and inexpensive intervention that may significantly reduce the risk of preterm birth. However, this possibility needs to be proven in a properly designed RCT with preterm birth as the primary outcome. Such a clinical trial in a racially, ethnically and geographically diverse population could best be accomplished through the established infrastructure of the Global Network for Women's and Children's Health Research (Global Network or GN).

## 2 METHODS

---

### 2.1 STUDY DESIGN

We propose a randomized, placebo-controlled, double-blinded multicenter clinical trial to assess the efficacy of LDA in the reduction of preterm birth. Women will be randomized equally to receive either daily LDA (81 mg) or an identical appearing placebo beginning between 6 0/7 weeks and 13 6/7 weeks GA and continuing until 36 0/7 weeks GA or delivery.

### 2.2 STUDY POPULATION

Studying the effect of LDA in women at very high risk for preterm birth (e.g., prior preterm birth) would have numerous confounders, as these women are likely to undergo interventions intended to decrease their risk. Conversely, multiparous women with prior term births would be at very low risk for preterm birth, making them a suboptimal study population. Nulliparous women appear to be the ideal population to study the effects of LDA since they will not undergo special interventions to avoid preterm birth. Multiple studies have shown that the risk of preterm birth in nulliparous women is higher than for the general obstetric population.

A total of 11,920 nulliparous women will be enrolled (5960 per group) across seven sites in sub-Saharan Africa, South Asia, and Latin America. For balance, each site will enroll no more than 25% of the total sample. To study the possible effect of LDA on anemia will enroll 500 women, with each site contributing at least 10% of the sample.

#### 2.2.1 Inclusion Criteria

- Nulliparous women between 18 – 40 years of age. Minors who are  $\geq$  14 years of age may be enrolled if permitted by the country's ethical guidelines.
- No more than two previous first trimester pregnancy losses
- No medical contraindications to aspirin;
- Single live intrauterine pregnancy (IUP) between 6 0/7 and 13 6/7 weeks GA corroborated by an early dating ultrasound and with presence of a heartbeat.

[figure not shown]
#### 2.2.2 Exclusion Criteria

- Women prescribed daily aspirin for more than 7 days;
- Multiple gestations;
- Fetal anomaly by ultrasound (Note most fetal anomalies are not detectable by ultrasounds done at this early gestation. Subsequent discovery of a fetal anomaly is not viewed as an exclusion.);
- Hemoglobin  $< 7.0$  g/dl at screening;
- Systolic blood pressure  $\geq 140$  and diastolic  $\geq 90$  at screening;
- Any other medical conditions that may be considered a contraindication per the judgment of the site investigator (e.g., Lupus, Type 1 Diabetes, or any other known significant disease)

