### **SECONDARY OUTCOMES:**

- ***Preeclampsia:*** characterized by hypertension and proteinuria occurring after the 20th week of pregnancy. Hypertension is a blood pressure of 140/90 mm Hg or above. In severe pre-eclampsia the diastolic blood pressure is usually 110 mm Hg or above and there may also be one or more of the following symptoms: severe headache, blurred vision, nausea and/or vomiting, abdominal pain and a diminished urinary output, i.e., oliguria. ***Early onset Preeclampsia*** develops before 34 weeks of gestation.
- ***Eclampsia:*** Very serious complication of pregnancy characterized by convulsions and coma. It may be preceded by signs of pre-eclampsia or the onset may be rapid and sudden. Eclamptic fits can occur in pregnancy, labour or soon after delivery.
- ***Small for gestational age:*** newborns with weights below the 10th percentile for gestational age.
- ***Perinatal mortality:*** The number of stillbirths and deaths in the first week of life per 1,000 live births, the perinatal period commences at 22 completed weeks (154 days) of gestation and ends seven completed days after birth.

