#### **3.2 Secondary Hypotheses and Associated Outcomes**

The study will also test three secondary hypotheses:

- Infants of women who take antenatal daily LDA initiated at 6 0/7 to 13 6/7 weeks GA will be at lower risk of being small for gestational age (SGA).
- Women who take antenatal daily LDA initiated at 6 0/7 to 13 6/7 weeks GA will have lower risk of: eclampsia and preeclampsia. Note that this hypothesis will be operationalized as evidence of hypertensive disorders of pregnancy as defined in more detail in Sections 9 and 12.
- Infants of women who take antenatal daily LDA initiated at 6 0/7 to 13 6/7 weeks GA will be at lower risk of perinatal mortality.

These secondary hypotheses will be tested using the following outcomes.

- Small for gestational age infants include newborns with weights below the 10th percentile for gestational age, as defined by Intergrowth Standards.
- Risk of Pregnancy Induced Hypertension (eclampsia and/or preeclampsia) defined as a binary outcome of any of new onset hypertension that occurs beyond 20 weeks gestational age, preeclampsia, or eclampsia happening between initiation of study dosing and participant completion of the study at 6 weeks after delivery. Eclampsia is a serious complication of pregnancy characterized by convulsions and coma. It may be preceded by signs of pre-eclampsia or the onset may be rapid and sudden and can occur in pregnancy, labor or soon after delivery. Preeclampsia is characterized by hypertension and proteinuria occurring after the 20th week of pregnancy. See Sections 9 and 12 for more detail.

- Perinatal mortality is a binary outcome that includes any stillbirth occurring after 20 weeks pregnancy and any early neonatal death that occurs within 7 days after delivery.

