Preeclampsia and eclampsia (or more appropriately hypertensive disorders of pregnancy)	Binary	
The unit of analysis is the woman randomized to the trial, but the outcome will be defined by the characterization of evidence of hypertensive disorder, including either preeclampsia or eclampsia occurring during the pregnancy. The algorithm for defining this endpoint is included as an addendum to this SAP in HypertensionAlgorithm_V1.1_10052018 (amendments to this algorithm may occur as part of the endpoint adjudication process and will be documented in new versions of this addendum accordingly).
 
 
• Briefly, any of the following will count as evidence of hypertensive disease: 
 
○ Any reported SAE of preeclampsia or eclampsia.
 
○ M NH registry report of hypertensive disease, preeclampsia or eclampsia.
 
○ Reports of elevated blood pressures that meet criteria based on the ACOG 2013 “Hypertension in Pregnancy” Task Force Report at any point after 20 weeks GA. 
 
▪ The only case that will programmatically qualify for evidence of hypertension is: Any individual with 2 consecutive timepoints with <math>\geq 140</math> mm Hg systolic or <math>\geq 90</math> mm Hg diastolic where those timepoints occur more than a week (7 days) apart. The criteria (e.g. elevated systolic or elevated diastolic) must be consistent for the two consecutive visits.
 
 
 
 
 
• For individuals that do meet the above criteria 
 
○ If they have less no reports of elevated blood pressure or a single report of elevated blood pressure that is followed by a normal value, they will not be considered to have evidence of hypertensive disease.
 
○ If they have any other reports of elevated blood pressure, their outcome classification will be adjudicated in a masked manner by clinical experts.
 
 
 
 
Will exclude any MTP but include withdrawals and terminations as data are available. Analysis Population: mITT
 
.

Variable	Type	Definition

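### Women with one blood-pressure component already raised can enter, and SAP 9.2 as shown does not keep them out of a hypertension outcome described as new onset

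*Combined protocol and SAP*

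**What the plan says.** **Entry.** Protocol 2.2.2 and SAP 4.2 use the same exclusion: "Systolic blood pressure $\geq 140$ and diastolic $\geq 90$ at screening". The two limits are joined by *and*. No other exclusion names hypertension, although a general clause leaves other medical conditions to the site investigator's judgment.

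**Outcome, as described.** SAP 3.2 defines the hypertensive secondary outcome as "any of new onset hypertension that occurs beyond 20 weeks gestational age, preeclampsia, or eclampsia", from the start of dosing to six weeks after delivery.

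**Outcome, as scored.** SAP 9.2 gives three routes to a case:
- a serious adverse event of preeclampsia or eclampsia;
- a "registry report of hypertensive disease, preeclampsia or eclampsia";
- raised blood pressure "at any point after 20 weeks GA".

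For the third route the programmed rule is two consecutive timepoints at or above 140 "mm Hg systolic or \geq 90 mm Hg diastolic where those timepoints occur more than a week (7 days) apart". It adds that "The criteria (e.g. elevated systolic or elevated diastolic) must be consistent for the two consecutive visits". Either component alone is enough, provided it is the same one both times.

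SAP 9.2 presents this as a summary of an algorithm held in a separate addendum. The outcome *preterm, preeclampsia* in SAP 9.2 is built on the same definition, restricted to delivery before 34 weeks.

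**The concern.** The entry rule and the scoring rule are not complements. A woman with an isolated systolic or isolated diastolic elevation is eligible, yet one of her components is already at the level that the outcome counts. If that component stays raised, she can become a case through hypertension that was there before the first tablet. Such a case does not fit SAP 3.2's own description, "new onset hypertension that occurs beyond 20 weeks gestational age".

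Treatment cannot prevent a condition already present at randomisation. These cases would fall about equally in both arms and pull the relative risk towards 1. They would also blur what the outcome means. The plan gives only 70% power for a 20% reduction in eclampsia/preeclampsia, so there is little room for dilution.

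**Working it through.** **1. The two rules applied to the same readings**

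| Reading | Entry rule (both components) | Outcome threshold (either component) |
|---|---|---|
| 150/85 | eligible | at or above |
| 135/95 | eligible | at or above |
| 150/95 | excluded | at or above |
| 135/85 | eligible | below |

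The first two rows are the gap.

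**2. Is the gap closed elsewhere?** SAP 3.2 contains the new-onset condition. The SAP 9.2 summary has no step that looks at blood pressure at entry, and its registry route has no onset condition. Protocol Appendix 3 says "Hypertension is a blood pressure of 140/90 mm Hg or above" and does not settle whether one component suffices. The hypertension addendum is not among the documents. Nothing available closes the gap.

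**3. The plan's own power figures.** Inputs from protocol 3.2 and SAP 6.2: 5,483 evaluable women per arm, 5% control risk, type I error 0.05 (taken as two-sided). With d = p1 − p2 and p̄ the mean of p1 and p2,

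power = Φ{[d − 1.96·√(2p̄(1−p̄)/n)] / √[(p1(1−p1) + p2(1−p2))/n]}.

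| Reduction | p1 vs p2 | Computed | With continuity correction | Plan |
|---|---|---|---|---|
| 20% | 5.0% vs 4.0% | 71.4% | 69.8% | 70% |
| 24% | 5.0% vs 3.8% | 86.5% | 85.5% | 85% |
| 26% | 5.0% vs 3.7% | 91.6% | 90.8% | 90% |

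The plan's figures reproduce.

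**4. Dilution, as an illustration.** Let p be the share of each arm that is a carried-in case, added to 5% (placebo) and 4% (aspirin, true relative risk 0.80).

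- Observed relative risk = (0.04 + p)/(0.05 + p)
- Carried-in share of placebo cases = p/(0.05 + p)

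| p | Observed relative risk | Share of placebo cases | Power |
|---|---|---|---|
| 0 | 0.80 | 0% | 71% |
| 0.5% | 0.045/0.055 = 0.82 | 0.005/0.055 = 9% | 67% |
| 1.0% | 0.050/0.060 = 0.83 | 0.010/0.060 = 17% | 63% |
| 1.5% | 0.055/0.065 = 0.85 | 0.015/0.065 = 23% | 60% |

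**5. What p might be.** The documents give no early-pregnancy blood-pressure distribution, so p cannot be estimated from them. Purely as an assumption, take a bivariate normal with correlation 0.6 and cut-points 139.5 and 89.5.

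- Low end (systolic mean 108, SD 11; diastolic mean 68, SD 8): exactly one component is raised in 0.50% of women, about 60 of 11,920.
- High end (systolic mean 112, SD 13; diastolic mean 70, SD 9.5): 2.88%, about 340 of 11,920.

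These are women who could pass entry with one raised reading. Only those who stay raised and meet the outcome rule contribute to p.

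**The case against.** **A threshold is not the outcome.** A reader might infer that the outcome starts with prevalent cases. The documents do not support that. One raised reading between 6 and 13 weeks is not a case. The programmed rule needs the same component raised at two consecutive timepoints after 20 weeks. A single raised value followed by a normal one does not count, and other patterns go to masked adjudication. Blood pressure is also listed on the biweekly form, so intermediate normal readings may break a run. This objection stands and limits the point to women who *can* be counted.

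**The addendum may already deal with it.** A baseline step there can be neither confirmed nor excluded. This stands, and it is why the fix allows the statement to be made in the addendum.

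**The size is assumed.** This stands in full. For p to be 0.5% at the low-end prevalence of 0.50%, every such woman would have to become a case. For p to be 1.5% at the high end of 2.88%, 52% would. No persistence rate is available. The 5% planning risk is also not described as net of pre-existing hypertension, so adding p to it may count some women twice. A higher base rate for the broader hypertensive outcome would shrink the effect.

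**The shift is small against sampling error.** At 5% versus 4% with 5,483 per arm, the standard error of the log relative risk is √(0.95/274.15 + 0.96/219.32) = 0.0886, so the 95% interval around 0.80 is about 0.67 to 0.95. SAP 7.5 treats secondary outcomes as exploratory. Both are fair reasons to rank the point low, but neither removes the mismatch.

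**The *and* may be loose wording, and investigators could exclude known hypertensives.** Both are possible. Neither is written as a rule for a woman with one raised component, and neither tells the analyst how to classify her.

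**Conclusion.** The mismatch is real and appears in both the protocol and the SAP. Women with one component at or above the outcome's own threshold can be randomised, and SAP 9.2 as shown would count them later if the elevation persists, despite the new-onset wording in SAP 3.2.

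The consequence is limited to dilution towards 1 of the hypertensive-disorder outcome and of *preterm, preeclampsia*. Someone might read it as bias between arms or as a threat to the main result. It is neither: randomisation balances these women, and preterm birth is defined by gestational age at delivery.

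The size is unknown. The illustrated movement from 0.80 to between 0.82 and 0.85 rests on an assumed 0.5% to 1.5% of each arm being carried-in cases, on a 5% risk that excludes them, and on no treatment effect in them.

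It is also tempting to conclude that the eligibility criterion should be reworded. SAP section 1 says randomisation was completed in summer 2018, so a new wording would exclude nobody and would misstate the rule under which women were enrolled. What remains is an inexpensive improvement to the analysis.

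**What to change.** Reconcile protocol 2.2.2 and SAP 4.2 with SAP 3.2 and SAP 9.2, leaving the eligibility text as it was used. Before unmasking:

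1. State in SAP 9.2, or in its hypertension addendum, how new onset is applied, including for the registry route. If the addendum already has a baseline step, cite it in SAP 9.2.
2. Use the blood pressure recorded at enrolment to flag women with either component at or above the threshold that SAP 9.2 itself uses. The Clinical Assessment form (protocol section 4) and Appendix 1 both list this measurement. If the screening value is held separately, say which reading defines the flag.
3. Report the number flagged by arm, and give the hypertensive-disorder and *preterm, preeclampsia* outcomes with and without the flagged women.

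This fits the masked data review in SAP 7.6, and SAP 9.2 already provides for documented amendments to the algorithm.

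The cost is one derived flag from data already collected, one extra analysis of two outcomes, and a slightly smaller denominator in that analysis. The count of flagged women would replace the assumed prevalence above with an observed one.
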